5.2. Second Course Phase

Second Course Phase	Treatment Cycles ^a									Post-Treatment		
Treatment Cycle/Title:	Entry into Second Course Phase	1	2	3	4	To be repeated beyond 7 cycles			Every 6-9 weeks	Post-Tx Safety Follow-Up Visit	Additional Follow-Up Visits	Survival Follow-Up
						5	6	7				
Scheduling Window (Days):	-28 to -1		± 3	± 3	± 3	± 3	± 3	± 3	From C1D1 ± 7	30 days (± 7 days) post last dose of study treatment	Suggested every 9 weeks x 1 year; then every 12 weeks	Approximately every 6 months from Post-Tx Safety Follow-up Visit
Medical History Review ^m	X											
Prior and Concomitant Medication Review	X	X	X	X	X	X	X	X		X		
Pembrolizumab Administration		X	X	X	X	X	X	X				
Post-treatment anticancer therapy status										X		X
Survival Status		X										
Review Adverse Events ^a		X	X	X	X	X	X	X		X		
Physical Examination, Weight and ECOG Performance Status	X	X ^b	X	X	X	X	X	X		X		
Vital Signs ^c	X	X	X	X	X	X	X	X		X		
ECHO (Echocardiogram)		X ^h										
Pregnancy Test – Urine or Serum -HCG ^d	X											
PT/INR and aPTT	X ^e											
CBC with Differential ^j	X ^l		X	X	X	X	X	X		X		
Comprehensive Serum Chemistry Panel ^{ij}	X ^l		X	X	X	X	X	X		X		
Urinalysis	X ^l											
T3, FT4 and TSH	X ^l											

Second Course Phase	Treatment Cycles ^a									Post-Treatment		
Treatment Cycle/Title:	Entry into Second Course Phase	1	2	3	4	To be repeated beyond 7 cycles			Every 6-9 weeks	Post-Tx Safety Follow- Up Visit	Additional Follow-Up Visits	Survival Follow-Up
						5	6	7				
Scheduling Window (Days):	-28 to -1		± 3	± 3	± 3	± 3	± 3	± 3	From C1D1 ± 7	30 days (± 7 days) post last dose of study treatment	Suggested every 9 weeks x 1 year; then every 12 weeks	Approximately every 6 months from Post-Tx Safety Follow-up Visit
Tumor Imaging and Assessments ^f	X								X		X	
Correlative Studies Blood Collection ^g	X			X		X		X		X		
Optional Studies Blood Collection ^k	X			X		X		X		X		

- Subjects will be followed for adverse events through 30 days after last dose of study treatment and for serious adverse events through 90 days after last dose of study treatment (or through 30 days if new anti-cancer therapy is initiated)
- C1D1 Physical Exam/Performance Status/Weight not required if done within 7 days of Entry into Second Course Phase exam.
- To include temperature, pulse rate, blood pressure, and either respiratory rate or oxygen saturation
- Collect within 72 hours prior to administration of study treatment in women of childbearing potential. If urine pregnancy results cannot be confirmed as negative, a serum pregnancy test will be required
- Must be done within 7 days of C1D1 if on anti-coagulants such as warfarin/heparin. Otherwise to be done within 10 days of C1D1.
- It is recommended that scans are performed within 28 days of re-initiation of pembrolizumab but the interval may be determined per the investigator. Scans will then be performed per investigator discretion at a recommended interval of every 6-9 weeks. Subjects who discontinue study treatment and have not had second documented disease progression or started new anti-cancer therapy should have tumor imaging per investigator discretion at a suggested frequency of every 9 weeks (±7 days) to monitor disease status. After 1 year of follow-up, tumor imaging can go from 9 to 12 week intervals per investigator discretion.
- Includes [(2) 8 ml CPT tubes, (1) 10 ml red top and (1) 10 ml purple top)]. Collect at Entry into Second Phase, prior to dose administration every other (odd numbered) cycle (starting with Cycle 3), and at second documented disease progression or at the Post-Treatment Safety Follow-up Visit
- Subjects who do not have symptoms of cardiac disease as determined by the investigator will have an echocardiogram to monitor LVEF every 5 years (± 90 days) from the last dose of doxorubicin. This is required regardless of the number of doxorubicin doses administered during the Initial Treatment Period. Subjects who develop symptoms of cardiac disease any time after initiation of doxorubicin will be referred to cardiology. In this case, the frequency of cardiac evaluations will be determined by cardiology.
- See Table 2 for complete list of required chemistries
- After cycle 1, pre-dose laboratory procedures can be conducted up to 72 hours prior to dosing
- Optional blood correlatives (1) 2.5 ml Paxgene only to be collected in subjects who consent. Collected at Entry into Second Phase, prior to dose administration every other (odd numbered) cycle (starting with Cycle 3), and at second documented disease progression or at the Post-Treatment Safety Follow-up Visit
- All Entry into Second Course Phase labs must be done within 10 days of C1D1

- m. To include baseline signs and symptoms present at the time of Entry into Second Course Phase
- n. Dosing interruptions are permitted in the case of medical/surgical events or logistical reasons not related to study treatment. However, subjects should be placed back on study treatment within 3 weeks of the scheduled interruption, unless otherwise discussed with the Sponsor-Investigator.

6. TREATMENT PLAN

6.1. Drug Dosage and Administration

The study drug (pembrolizumab) must be exclusively used for the investigation specified in this protocol and it will only be accessible to authorized staff. Treatment with doxorubicin IV and pembrolizumab IV will be administered every 3 weeks (21 days) +/- 3 days during the Initial Treatment Period. Day 1 of the cycle will be defined as the day that pembrolizumab is administered. In the event of a delay in pembrolizumab administration, doxorubicin may be continued to be administered every 21 days. This may result in more than one doxorubicin administration within a cycle. In the event of doxorubicin discontinuation due to toxicity, pembrolizumab will be allowed to continue until any of the criteria in Section 6.11 are met. In the event that the maximum allowable doxorubicin dosage of 450 mg/m² is reached and no toxicity has occurred, subjects will discontinue treatment with doxorubicin, but will continue treatment with pembrolizumab until any of the criteria in Section 6.11 are met. In the event of toxicity requiring discontinuation of pembrolizumab, treatment with doxorubicin on study will be discontinued. Subjects in the Second Course Phase will receive monotherapy pembrolizumab every 3 weeks (21 days) +/- 3 days.

Table 3. Drug dose and administration

Drug	Dose/ Potency	Dose Frequency	Route of Administration	Regimen/Treatment Period
Pembrolizumab ^a	200 mg or 2mg/kg (up to 200 mg) ^d	Q3W	IV infusion	Day 1 of each 3 week cycle
Doxorubicin ^b	60- 75 mg/m ² ^c Cycle 1 Day dose = 60 mg/m ²	Q3W	IV injection	Day 1 of each 3 week cycle 1

- a Sites should make every effort to target infusion timing to be as close to 30 minutes as possible. However, given the variability of infusion pumps from site to site, a window of -5 and +10 minutes is permitted. A sterile, non-pyrogenic, low-protein binding 0.2 to 5 µm in-line filter made of polyethersulfone (PES) must be used during administration to remove any adventitious particles. If the infusion set does not contain 0.2 to 5 µm in-line filter, it is recommended to use 0.2 to 5 µm add-on filter which may contain an extension line
- b A single, 12mg dose of dexamethasone may be given prior to administration of doxorubicin. Administer doxorubicin intravenously over 10 (± 5) minutes. Decrease the rate of doxorubicin administration if erythematous streaking along the vein proximal to the site of infusion or facial flushing occurs. Dexrazoxane may be administered at a 10:1 ratio (dexrazoxane: doxorubicin) at the investigator's discretion, within 30 minutes prior to each doxorubicin infusion for prevention of cardiotoxicity. **It is recommended that all subjects receiving 5 or more cycles of doxorubicin receive dexrazoxane.**
- c All subjects should initiate doxorubicin at a dose of 60 mg/m² at Cycle 1 Day 1. Dose may be escalated to 75 mg/m² per investigator discretion after Cycle 1. Total dose of doxorubicin should not exceed cumulative lifetime dose of 450 mg/m².

- d Subjects 18 years of age or older will receive 200 mg IV every 3 weeks. Subjects 12-17 years of age will receive 2 mg/kg IV (calculated from weight at screening) (up to 200 mg) every 3 weeks. If the subject's (aged 12-17 years old) weight changes by more than 10% from the screening weight, the pembrolizumab dose should be recalculated. Subjects who turn 18 during treatment will receive the 200 mg dose after the 18th birthday.

Study treatment will begin on the day of enrollment. Study treatment will continue until any of the criteria in Section 6.11 are met. Subjects who stop treatment with pembrolizumab in the Initial Treatment Period may be retreated if they meet the criteria specified in Section 7.

The investigator shall take responsibility for and shall take all steps to maintain appropriate records and ensure appropriate supply, storage, handling, distribution and usage of study drug in accordance with the protocol and any applicable laws and regulations.

6.2. Dose Selection

The rationale for selection of doses to be used in this trial is provided in Section 2.3. Details on preparation and administration of pembrolizumab (MK-3475) are provided in the Pharmacy Manual.

6.3. Dose Modification for Doxorubicin

Dose modifications to the administration of doxorubicin will be allowed per package insert. Pembrolizumab may be given if doxorubicin is held for toxicity, at the discretion of the Investigator.

6.4. Toxicity-Related Dose Delays/Dose Modifications/Discontinuations for Pembrolizumab

If a dose of pembrolizumab is withheld for toxicity, then subjects may resume dosing with pembrolizumab if that is appropriate at their next scheduled appointment or when toxicity has improved as described below.

Pembrolizumab will be withheld for \geq Grade 3 drug-related toxicity including laboratory abnormalities and severe or life-threatening AEs per Table 4.

Growth factors are allowed for hematologic toxicities.

In case toxicity does not resolve to Grade 0-1 within 12 weeks after last infusion, pembrolizumab should be discontinued after consultation with the Sponsor-Investigator. Subjects who require corticosteroids to manage drug-related adverse events must be at an equivalent dose of ≤ 10 mg per day of prednisone to resume dosing with pembrolizumab. Furthermore, an inability to reduce the corticosteroid dose for managing a drug-related adverse event to the equivalent of ≤ 10 mg prednisone per day

within 12 weeks of last pembrolizumab dose should prompt discussion with the Sponsor-Investigator regarding the subject's ability to continue on treatment in the trial. Subjects with a laboratory adverse event still at Grade 2 after 12 weeks may continue treatment in the trial only if asymptomatic and controlled. This includes subjects who experience drug induced hypothyroidism requiring replacement therapy. Resumption of pembrolizumab may occur once the subject is stable on adequate doses of replacement therapy and is clinically asymptomatic.

For subjects who experience a recurrence of the same AE(s) at the same grade or greater with rechallenge of pembrolizumab, a discussion should occur to determine whether the subject should continue in the trial. However, for a subject who experiences a recurrence of the same serious adverse event at the same grade or greater with rechallenge of pembrolizumab, the subject **MUST** discontinue study treatment. Dose increase or decrease of pembrolizumab will not be permitted in individual subjects.

6.5. Dose Modification and toxicity management for immune-related AEs associated with pembrolizumab and combination therapy

Adverse events (both non-serious and serious) associated with pembrolizumab exposure may, including coadministration with additional compounds, represent an immunologic etiology. These adverse events may occur shortly after the first dose of pembrolizumab/combination treatment or several months after the last dose of treatment and may affect more than one body system simultaneously. Therefore, early recognition and initiation of treatment is critical to reduce complications. Based on existing clinical study data, most irAEs were reversible and could be managed with interruptions of pembrolizumab/combination treatment, administration of corticosteroids and/or other supportive care. For suspected irAEs, ensure adequate evaluation to confirm etiology or exclude other causes. Pembrolizumab must be withheld for drug-related toxicities and severe or life-threatening AEs as per below. Doxorubicin should be given as described in Section 6.1 if pembrolizumab is withheld for toxicity.

Table 4. Dose Modification and Toxicity Management for Immune-related Adverse Events Associated with Pembrolizumab monotherapy and IO Combinations.

General instructions:

1. Severe and life-threatening irAEs should be treated with IV corticosteroids followed by oral steroids. Other immunosuppressive treatment should begin if the irAEs are not controlled by corticosteroids.
2. Pembrolizumab must be permanently discontinued if the irAE does not resolve or the corticosteroid dose is not ≤ 10 mg/day within 12 weeks of the last pembrolizumab treatment.
3. The corticosteroid taper should begin when the irAE is \leq Grade 1 and continue at least 4 weeks.
4. If pembrolizumab has been withheld, pembrolizumab may resume after the irAE decreased to \leq Grade 1 after corticosteroid taper.

irAEs	Toxicity Grade (CTCAE v4.0)	Action With Pembrolizumab	Corticosteroid and/or Other Therapies	Monitoring and Follow-up
Pneumonitis	Grade 2	Withhold	
 Administer corticosteroids (initial dose of 1 to 2 mg/kg prednisone or equivalent) followed by taper Add prophylactic antibiotics for opportunistic infections 	
 Monitor participants for signs and symptoms of pneumonitis Evaluate participants with suspected pneumonitis with radiographic imaging and initiate corticosteroid treatment
	Recurrent Grade 2, Grade 3 or 4	Permanently discontinue		
Diarrhea/Colitis	Grade 2 or 3	Withhold	
 Administer corticosteroids (initial dose of 1 to 2 mg/kg prednisone or equivalent) followed by taper 	
 Monitor participants for signs and symptoms of enterocolitis (ie, diarrhea, abdominal pain, blood or mucus in stool with or without fever) and of bowel perforation (ie, peritoneal signs and ileus) Participants with \geqGrade 2 diarrhea suspecting colitis should consider GI consultation and performing endoscopy to rule out colitis Participants with diarrhea/colitis should be advised to drink liberal quantities of clear fluids. If sufficient oral fluid intake is not feasible, fluid and electrolytes should be substituted via IV infusion
	Recurrent Grade 3 or Grade 4	Permanently discontinue		

AST or ALT Elevation or Increased Bilirubin	Grade 2 ^a	Withhold	
 Administer corticosteroids (initial dose of 0.5 to 1 mg/kg prednisone or equivalent) followed by taper 	
 Monitor with liver function tests (consider weekly or more frequently until liver enzyme value returned to baseline or is stable)
	Grade 3 ^b or 4 ^c	Permanently discontinue	
 Administer corticosteroids (initial dose of 1 to 2 mg/kg prednisone or equivalent) followed by taper 	
T1DM or Hyperglycemia	New onset T1DM or Grade 3 or 4 hyperglycemia associated with evidence of β -cell failure	Withhold ^d	
 Initiate insulin replacement therapy for participants with T1DM Administer antihyperglycemic in participants with hyperglycemia 	
 Monitor participants for hyperglycemia or other signs and symptoms of diabetes
Endocrine disorders- other (hypophysitis)	Grade 2	Withhold	
 Administer corticosteroids and initiate hormonal replacements as clinically indicated 	
 Monitor for signs and symptoms of hypophysitis (including hypopituitarism and adrenal insufficiency)
	Grade 3 or 4	Withhold or permanently discontinue ^d		
Hyperthyroidism	Grade 2	Continue	
 Treat with nonselective beta-blockers (eg, propranolol) or thionamides as appropriate 	
 Monitor for signs and symptoms of thyroid disorders
	Grade 3 or 4	Withhold or permanently discontinue ^d		
Hypothyroidism	Grade 2, 3 or 4	Continue	
 Initiate thyroid replacement hormones (eg, levothyroxine or liothyronine) per standard of care 	
 Monitor for signs and symptoms of thyroid disorders
Nephritis: grading according to increased creatinine or acute kidney injury	Grade 2	Withhold	
 Administer corticosteroids (prednisone 1 to 2 mg/kg or equivalent) followed by taper 	
 Monitor changes of renal function
	Grade 3 or 4	Permanently discontinue		
Neurological Toxicities	Grade 2	Withhold		

	Grade 3 or 4	Permanently discontinue	
 Based on severity of AE administer corticosteroids 	
 Ensure adequate evaluation to confirm etiology and/or exclude other causes
Myocarditis	Grade 1	Withhold	
 Based on severity of AE administer corticosteroids 	
 Ensure adequate evaluation to confirm etiology and/or exclude other causes
	Grade 2, 3 or 4	Permanently discontinue		
Exfoliative Dermatologic Conditions	Suspected SJS, TEN, or DRESS	Withhold	
 Based on severity of AE administer corticosteroids 	
 Ensure adequate evaluation to confirm etiology or exclude other causes
	Confirmed SJS, TEN, or DRESS	Permanently discontinue		
All Other irAEs	Persistent Grade 2	Withhold	
 Based on severity of AE administer corticosteroids 	
 Ensure adequate evaluation to confirm etiology or exclude other causes
	Grade 3	Withhold or discontinue based on the event ^c		
	Recurrent Grade 3 or Grade 4	Permanently discontinue		

AE(s)=adverse event(s); ALT= alanine aminotransferase; AST=aspartate aminotransferase; CTCAE=Common Terminology Criteria for Adverse Events; DRESS=Drug Rash with Eosinophilia and Systemic Symptom; GI=gastrointestinal; IO=immuno-oncology; ir=immune related; IV=intravenous; SJS=Stevens-Johnson Syndrome; T1DM=type 1 diabetes mellitus; TEN=Toxic Epidermal Necrolysis; ULN=upper limit of normal.

Note: Non-irAE will be managed as appropriate, following clinical practice recommendations.

^a AST/ALT: >3.0 to 5.0 x ULN if baseline normal; >3.0 to 5.0 x baseline, if baseline abnormal; bilirubin:>1.5 to 3.0 x ULN if baseline normal; >1.5 to 3.0 x baseline if baseline abnormal

^b AST/ALT: >5.0 to 20.0 x ULN, if baseline normal; >5.0 to 20.0 x baseline, if baseline abnormal; bilirubin:>3.0 to 10.0 x ULN if baseline normal; >3.0 to 10.0 x baseline if baseline abnormal

^c AST/ALT: >20.0 x ULN, if baseline normal; >20.0 x baseline, if baseline abnormal; bilirubin: >10.0 x ULN if baseline normal; >10.0 x baseline if baseline abnormal

^d The decision to withhold or permanently discontinue pembrolizumab is at the discretion of the investigator or treating physician. If control achieved or ≤ Grade 2, pembrolizumab may be resumed.

^e Events that require discontinuation include, but are not limited to: encephalitis and other clinically important irAEs (eg, vasculitis and sclerosing cholangitis).

Dosing interruptions are permitted in the case of medical / surgical events or logistical reasons not related to study treatment (e.g., elective surgery, unrelated medical events, patient vacation, and/or holidays). Subjects should be placed back on study treatment within 3 weeks of the scheduled interruption, unless otherwise discussed with the

Sponsor-Investigator. The reason for interruption should be documented in the subject's study record.

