 - For **Grade 3 or 4 diarrhea/colitis**, treat with intravenous steroids followed by high dose oral steroids.
 - When symptoms improve to Grade 1 or less, steroid taper should be started and continued over no less than 4 weeks.

- **Type 1 diabetes mellitus (if new onset, including diabetic ketoacidosis [DKA]) or \geq Grade 3 Hyperglycemia, if associated with ketosis (ketonuria) or metabolic acidosis (DKA)**
 - For **T1DM** or **Grade 3-4 Hyperglycemia**
 - Insulin replacement therapy is recommended for Type I diabetes mellitus and for Grade 3-4 hyperglycemia associated with metabolic acidosis or ketonuria.
 - Evaluate subjects with serum glucose and a metabolic panel, urine ketones, glycosylated hemoglobin, and C-peptide.
- **Hypophysitis:**
 - For **Grade 2** events, treat with corticosteroids. When symptoms improve to Grade 1 or less, steroid taper should be started and continued over no less than 4 weeks. Replacement of appropriate hormones may be required as the steroid dose is tapered.
 - For **Grade 3-4** events, treat with an initial dose of IV corticosteroids followed by oral corticosteroids. When symptoms improve to Grade 1 or less, steroid taper should be started and continued over no less than 4 weeks. Replacement of appropriate hormones may be required as the steroid dose is tapered.
- **Hyperthyroidism or Hypothyroidism:**

Thyroid disorders can occur at any time during treatment. Monitor subjects for changes in thyroid function (at the start of treatment, periodically during treatment, and as indicated based on clinical evaluation) and for clinical signs and symptoms of thyroid disorders.

 - **Grade 2** hyperthyroidism events (and **Grade 2-4** hypothyroidism):
 - In hyperthyroidism, non-selective beta-blockers (e.g. propranolol) are suggested as initial therapy.
 - In hypothyroidism, thyroid hormone replacement therapy, with levothyroxine or liothyronine, is indicated per standard of care.
 - **Grade 3-4** hyperthyroidism
 - Treat with an initial dose of IV corticosteroid followed by oral corticosteroids. When symptoms improve to Grade 1 or less, steroid taper should be started and continued over no less than 4 weeks. Replacement of appropriate hormones may be required as the steroid dose is tapered.
- **Hepatic:**
 - For **Grade 2** events, monitor liver function tests more frequently until returned to baseline values (consider weekly).
 - Treat with IV or oral corticosteroids

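### Section 6.4 and Table 4 disagree on when pembrolizumab stops or is held at three points, and the study calendars omit the periodic thyroid monitoring that Section 6.8.1 calls for.

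*Combined protocol and SAP*

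**What the plan says.** Stopping and holding rules for pembrolizumab appear in two places.

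- **Section 6.4** covers drug-related toxicity in general. For unresolved toxicity: "In case toxicity does not resolve to Grade 0-1 within 12 weeks after last infusion, pembrolizumab should be discontinued after consultation with the Sponsor-Investigator". If the steroid dose cannot be brought down to 10 mg/day of prednisone equivalent or less, that failure "within 12 weeks of last pembrolizumab dose should prompt discussion with the Sponsor-Investigator regarding the subject's ability to continue on treatment in the trial". It then adds: "Subjects with a laboratory adverse event still at Grade 2 after 12 weeks may continue treatment in the trial only if asymptomatic and controlled". Drug-induced hypothyroidism on replacement is named as falling under that allowance, and pembrolizumab may restart once the subject is stable on replacement and free of symptoms.
- **Section 6.5, Table 4** covers immune-related adverse events (irAEs). General instruction 2 reads: "Pembrolizumab must be permanently discontinued if the irAE does not resolve or the corticosteroid dose is not ≤ 10 mg/day within 12 weeks", with the clock again running from the most recent pembrolizumab dose. The hypothyroidism row covers Grades 2, 3 and 4. Its action is to continue pembrolizumab, with the therapy entry "Initiate thyroid replacement hormones (eg, levothyroxine or liothyronine) per standard of care".

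On thyroid monitoring, Section 6.8.1 says: "Monitor subjects for changes in thyroid function (at the start of treatment, periodically during treatment", and adds testing when clinical evaluation calls for it. Section 4.4 makes the calendars in Sections 5.1 and 5.2 the laboratory schedule. Each calendar has one mark in its T3, FT4 and TSH row: at Screening in 5.1 and at Entry into Second Course Phase in 5.2.

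**The concern.** An irAE treated with steroids is also a drug-related toxicity, so it falls under both sections. A site that reads Section 6.4 may discuss continuation in a case where Table 4 requires a permanent stop. Section 16.1 demands strict adherence to every specification, which is impossible when two specifications differ and neither is said to prevail.

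Safety is what this trial is designed to assess. Treatment administration is a safety endpoint (Section 12.2.6) and adverse event incidence is summarized (Section 12.7). If handling depends on which section a site follows, discontinuation and exposure figures partly reflect that choice. The decision can also reach the second drug: under Section 6.1, toxicity that requires pembrolizumab to be discontinued ends doxorubicin on study as well. For thyroid function, a site following the calendar has no scheduled on-treatment test, so finding a symptomless change depends on local practice.

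**Working it through.** The point is textual, so the check sets the rules side by side.

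| Situation | Section 6.4 | Table 4 (Section 6.5) | Compatible? |
|---|---|---|---|
| (a) Steroid dose above 10 mg/day at 12 weeks from last dose | Discussion about continuing | Permanent stop, no exception | No |
| (b) Laboratory irAE still Grade 2 at 12 weeks, asymptomatic and controlled | May continue | Permanent stop if unresolved, no exception | No |
| (c) Hypothyroidism, Grade 2 to 4 | Restart once stable on replacement, which implies a hold | Continue; no hold provided | No |

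**(a)** Threshold and clock are the same in both places. Only the consequence differs.

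**(b)** Take an immune-related Grade 2 AST or ALT elevation. Table 4 withholds pembrolizumab at Grade 2. If the value is still Grade 2 at 12 weeks, instruction 2 requires a permanent stop, while Section 6.4 allows treatment to continue if the subject has no symptoms and the event is controlled. This takes resolution to mean Grade 1 or lower, the level used in Section 6.4 and in Table 4 instruction 4. Footnote d relaxes the restart level for certain endocrine rows but is not attached to the AST/ALT row.

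**(c)** A restart presupposes an interruption, and the Table 4 row provides for none.

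**(d) Thyroid tests.** In calendar 5.1 the thyroid row has no mark in Cycles 1 to 7 or after treatment. The pattern repeated beyond Cycle 7 therefore adds none, giving 0 scheduled on-treatment tests over up to 35 administrations (Section 6.11). Calendar 5.2 also has none after entry, over up to one year at 3-week intervals (52/3, about 17 cycles). The neighbouring CBC and chemistry rows keep their marks from Cycle 2 onward, so loss of thyroid marks in text extraction is unlikely.

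**Reach of the doxorubicin link.** Assume full doses every 3 weeks without delay or reduction, and the 450 mg/m² ceiling.

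- At 60 mg/m² throughout: 7 × 60 = 420 and 8 × 60 = 480, so seven full doses, the last at week 6 × 3 = 18.
- At 75 mg/m² from Cycle 2: 60 + 5 × 75 = 435 and 60 + 6 × 75 = 510, so six full doses, the last at week 5 × 3 = 15.

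The 12-week limit can fall while doxorubicin is still due only if the last pembrolizumab dose was given by week 18 − 12 = 6, or week 15 − 12 = 3, respectively. Doxorubicin delays or reductions would widen that window.

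**The case against.** Several stronger readings are tempting, and the documents do not carry them.

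- **Same toxicity, opposite handling.** Section 6.4 also requires a steroid dose of 10 mg/day or less before pembrolizumab resumes. A subject above that level at 12 weeks with the drug withheld cannot restart at that moment under either section. The difference in (a) is a permanent stop against a discussion that leaves later resumption open.
- **Every irAE lasting beyond 12 weeks is affected.** For most unresolved toxicity Section 6.4 also says to discontinue, after consultation, which is close to Table 4. What remains of (b) is the Grade 2 laboratory allowance. Its named example, hypothyroidism on replacement, ends in continued dosing under the Table 4 row too.
- **The general hold at Grade 3 or above contradicts the hypothyroidism row.** That sentence covers "Grade 3 drug-related toxicity including laboratory abnormalities and severe or life-threatening AEs per Table 4". Its closing reference can be read as deferring to the row, so the contradiction is not established on that sentence. The tension in (c) rests on the restart wording alone.
- **Section 6.8.1 is a third source of stopping rules.** For dose modification it refers the reader to Section 6.5. Its part here is thyroid monitoring only.
- **No scheduled tests means no tests.** Section 6.8.1 offers suggested measures, sets no interval, and allows testing on clinical grounds. Unscheduled tests remain possible. What is missing is any scheduled test to match the periodic element.
- **The primary stopping rule is distorted.** Section 12.2.1 counts only events that are serious, drug-related, and judged clinically significant by the Sponsor-Investigator. Symptomless biochemical thyroid changes would generally not qualify, and no effect on the rule has been shown.

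Scope also differs: Section 6.4 covers all drug-related toxicity and Table 4 covers irAEs. That limits the overlap but does not remove it, since steroid-managed drug-related events and drug-induced hypothyroidism can fall under both.

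**Conclusion.** The point stands in a limited form. Section 6.4 and Table 4 are inconsistent at (a), (b) and (c), with (c) the weakest because it rests on an implied hold. The calendars and Section 6.8.1 are inconsistent on thyroid monitoring.

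Points (a) to (c) reach three groups: subjects still above the steroid limit at 12 weeks, those with a symptomless, controlled Grade 2 laboratory irAE at 12 weeks, and those with Grade 2 to 4 hypothyroidism. The documents give no expected frequency for any of these, so no count is offered. Point (d) applies to every treated subject, up to 30. What is at stake is consistency in pembrolizumab discontinuation, exposure and general adverse event summaries, plus on-study doxorubicin where the 12-week limit falls early enough.

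The conclusion assumes that no precedence rule exists outside the text reviewed and that the single thyroid marks reflect the calendars as issued. It should be corrected by amendment; it does not undermine the primary analysis.

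**What to change.** 1. Reconcile Section 6.4 with Table 4 on the 12-week steroid limit, the Grade 2 laboratory allowance, and whether hypothyroidism involves a hold.
2. State which of the two governs when an event is both drug-related and immune-related.
3. Reconcile the T3, FT4 and TSH rows of calendars 5.1 and 5.2 with Section 6.8.1, so that what is asked for and what is scheduled agree.

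Which rule to adopt is for the sponsor's clinical team; none is proposed here. The event-specific rows of Table 4 need not be merged to achieve this.

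Items 1 and 2 cost amendment wording only. If item 3 is settled by adding tests, the assays could use blood draws already scheduled from Cycle 2 onward, so the added burden is small.
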